9.3.1 Events not to be treated as AEs

- Preplanned interventions or occurrence of endpoints specified in the study protocol are not considered AEs, if not defined otherwise (e.g. as a result of overdose)
- Medical or surgical procedures, e.g., surgery, endoscopy, tooth extraction, transfusion that are not associated with the indication under study. However, the event leading to the procedure is considered an AE. If this event is serious, the procedure must be described in the SAE narrative.
- Pre-existing disease or medical condition prior to the screening visit that does not worsen
- Situations in which an adverse event change did not occur. In addition, the following reasons for hospitalizations are not considered AEs, and therefore not SAEs:
 - Hospitalizations for cosmetic elective surgery, social and/or convenience reasons. Treatment, which were elective or pre-planned, treatments for a pre-existing condition that is unrelated to the indication under study and did not worsen.
 - Standard monitoring of a pre-existing disease or medical condition that did not worsen, e.g., hospitalization for coronary angiography in a subject with stable angina pectoris
 - Elective treatment of a pre-existing disease or medical condition that did not worsen, e.g., elective hip replacement for arthritis
 - Routine treatment or monitoring of the studied indication, not associated with any deterioration in condition
 - Admission to a hospital or other institution for general care, not associated with any deterioration in condition; or treatment on an emergency, outpatient basis for an event not fulfilling any of the definitions of serious and not resulting in hospital admission

9.3.2 Events not to be treated as SAEs

Due to the seriousness of the disease in this study, certain conditions defined as SAEs will be excluded from expedited reporting on a SAE report form.

- Elective hospitalization and surgery for treatment of the underlying disease including transfusions
- Elective hospitalization to simplify treatment or study procedures

- Events that are only and unequivocally caused by progression of the underlying disease, except transformation to AML which is always to be reported as an SAE

Primary disease progression and related SAEs, e.g., hospitalization for surgery/diagnostic procedures, except for life-threatening status or death caused by the underlying malignant disease will not be considered and reported as SAEs if they are unrelated to study medication according to the investigator. The assessment of relationship to study medication must also be documented.

Further information on safety reporting can be found in the study specific Safety Management Plan.

9.4 Investigator reporting responsibilities

The investigator must keep copies of all AE information, including correspondence with the sponsor and the EC/IRB, on file. The investigator will be responsible for notifying regulatory bodies and ECs/CECs/IRBs as locally required.

The Investigator is obligated to report any SAE/pregnancy to the Sponsor within **24 hours** of becoming aware of the event to ensure the safety of all participants in the study and to meet regulatory reporting requirements. Although all information required for completion of an SAE report form may not be available within the specified time period, an initial report should be submitted with the available information. Any new information obtained about the serious adverse event must be added to the existing eCRF form.

The investigators report all occurring events electronically by completing the designated page in the eCRF system. A backup paper report form is provided to all sites as well. In case the eCRF cannot be accessed for any reasons, the SAE should be reported by completing and signing the paper backup form. The signed form will then be sent to:

Address: [REDACTED]
[REDACTED]
[REDACTED]
Phone: [REDACTED]
Fax: [REDACTED]
Email: [REDACTED]

Information on the form must be transferred to the eCRF by the site when it is accessible again. Each SAE and pregnancy must be followed up until resolution or stabilization by submission of updated reports (FU-report) to the designated recipient.

9.5 Sponsors reporting responsibilities

In accordance with Clinical Trial Regulation 536/2014 the sponsor should promptly notify all concerned investigators, institutions and the regulatory authorities of SUSARs and all findings that could affect adversely the safety of subjects, impact the conduct of the study or alter IEC/authority approval to continue the study. The sponsor will inform all trial sites about reported relevant changes of the benefit-risk ratio (e.g., occurrence of SUSARs) according to all applicable regulations.

Reporting of SUSAR by the Sponsor to the European Eudravigilance database (Article 42 CTR)

536/2014)

Sponsor of a clinical trial performed in at least one European member state shall report electronically and without delay to the Eudravigilance database all relevant information about the following SUSARs:

- a) all SUSARs from this clinical trial, irrespective of its location (site in the European Union or in a third country);
- b) all SUSAR related to the same active substance, regardless of pharmaceutical form and strength or indication investigated, in investigational medicinal products used in the clinical trial, occurring in a clinical trial performed exclusively in a third country, if that clinical trial is sponsored: by that sponsor, or by another sponsor who is either part of the same parent company as the sponsor of the clinical trial, or who develops a medicinal product jointly, on the basis of a formal agreement, with the sponsor of the clinical trial;
- c) all SUSARs to investigational medicinal products occurring in any of the subjects of the clinical trial, which are identified by or come to the attention of the sponsor after the end of the clinical trial.

The period for the reporting of SUSAR depends on the seriousness of the reaction:

- in the case of fatal or life-threatening SUSAR, as soon as possible and in any event not later than 7 days after the sponsor became aware of the reaction. If the initial report is incomplete, the sponsor shall submit a completed report based on the initial information within an additional 8 days;
- in the case of non-fatal or non-life-threatening SUSAR, not later than 15 days after the sponsor became aware of the reaction;
- in the case of a SUSAR which was initially considered to be non-fatal or non- life threatening but which turns out to be fatal or life-threatening, as soon as possible and in any event not later than 7 days after the sponsor became aware of the reaction being fatal or life-threatening;
- If significant new information on an already reported case is received by the sponsor, this information shall be reported as a follow-up report within 15 days.

More specifics about how safety reporting will be carried out in all participating countries is defined in the Safety Management Plan and safety agreements and contracts.

9.6 Development Safety Update Report (DSUR)

Once a year, the sponsor will supply a report on the safety of study subjects – development safety update report - in accordance with ICH E2F and ICH GCP with all relevant information during the reference period to the competent authority and the responsible ethics committee.

The date of the first approval of the study by a competent authority is the reference date for the start of the year which the annual safety report covers. Data lock point will be the last day of this year. The sponsor will supply the report within 60 days after the data lock point.

Further details will be given in the study-specific Safety Management Plan.

9.7 Reporting of serious breaches

The sponsor must report serious breaches of the EU Regulation 536/2014 or of the protocol (the version that is valid at the time of the breach) no later than seven days of awareness of the breach. Wherever a serious breach is suspected by the investigator, this must be reported to the sponsor within 24 hours to:

Email: [REDACTED]

A serious breach is defined as a breach likely to affect to a significant degree the safety and rights of a subject or the reliability and robustness of the data generated in the clinical trial.

10 Statistical methods and sample size calculation

The analytical methods presented below summarize the more complete plans to be detailed in a separate document in the statistical analysis plan (SAP). A change to the data analysis methods described in the protocol will require a protocol amendment only if it alters a principal feature of the protocol. A statistical analysis plan (SAP) must be written and finalized before database closure and statistical analysis for the interim analysis. The SAP must provide full details of the analyses, the data displays, and the algorithms to be used for data derivations.

10.1 General statistical considerations

No confirmatory statistical analysis will be conducted due to the changes described in section 5 and section 7.1. All analysis will be only explorative.

Statistical analysis will be performed using SAS® version 9.4 or higher.

Summary statistics (arithmetic mean, standard deviation, median, minimum, and maximum for quantitative variables) will be presented by the treatment group. Frequency tables for categorical data will be provided. Medical history findings will be summarized using MedDRA terms.

Missing values will not be imputed. Outliers will be identified prior to the analyses of the efficacy endpoints and have to be checked by the study physician. According to the decision of the data management, the statistician and the study physician, outliers will be kept in the database or set to "missing".

10.2 Analysis sets

10.2.1 Full Analysis Set (FAS)

The Full Analysis Set (FAS) consists of all patients who received at least one dose of study drug and fulfilled the inclusion criteria. The FAS is the primary dataset for analysis.

10.2.2 Per Protocol Set (PPS)

The Per Protocol Set (PPS) will be defined as the subset of patients of the FAS that reached study [REDACTED] and who have no major protocol deviations as to be determined on a per-subject basis immediately before data base lock.

10.2.3 Safety Evaluation Set (SES)

Safety summaries will be based on the Safety Evaluation Set, which will consist of all patients who received at least one dose of study drug.

10.3 Sample size calculation

The study was designed as single-arm phase II trial. The design of the trial focused on demonstrating that the efficacy is greater than an undesired level of efficacy (p_0) which would indicate that the treatment is ineffective. A Simon's two-stage design was used to allow for initial assessment of efficacy. The sample size calculation was based on the following assumptions.

- Given Null hypothesis $H_0: p \leq p_0$
- Alternative hypothesis $H_1: p > p_0$
- Level of inefficacy $p_0 = 0.05$
- Expected true response rate $p_1 = 0.2$
- Type-1-error $\alpha = 0.05$, one-sided
- Type-2-error $\beta = 0.1$

The null hypothesis that the true response rate is 0.05 was planned to be tested against a one-sided alternative. In the first stage, 10 patients were accrued. If there were 1 or fewer responses in these 10 patients, the study should be stopped. Otherwise, it was planned to accrue 10 additional patients for a total of 20. The null hypothesis would be rejected in favor of the alternative hypothesis if 5 or more responses are observed in 20 patients. This design yielded a one-sided type I error rate of no more than 0.05 and power of at least 0.9 when the true response rate is 0.2. To account for a loss of follow up of ~10%, enrollment of up to 22 patients is expected. Similarly, a total of 22 patients were planned to be enrolled prior to the interim analysis to ensure 20 evaluable patients for the interim analysis.

██████████ Due to potential benefits for the patients, the study will continue in an exploratory approach with change dose frequency as described in section 7.1.

10.4 Randomization / Stratification

This is an open-label, single-arm trial. Therefore, randomization and blinding techniques are not applicable.

10.5 Subject disposition

An accounting of study patients by disposition will be tabulated in each analysis population by treatment regimen (once in a [REDACTED] cycle for at least [REDACTED] cycles vs. [REDACTED] in a [REDACTED] (once every [REDACTED] days) for at least [REDACTED] cycles). A patient flow chart will be provided including the following information:

Number of subjects

- screened,
- screen failure,
- enrolled,
- treated.

- discontinued (along with primary reason for discontinuation) including primary treatment phase and extension phase,
- completed.

A summary of subjects enrolled by site will be provided. Protocol deviations will be listed.

10.6 Patient characteristics

Age, height, weight, BMI, gender, race and baseline hematology parameters will be summarized in a descriptive manner. The sum of transfusions required during the 16 weeks immediately preceding the first IMP administration and descriptive statistics for the sum will be calculated. Medical history data will be summarized using frequency tabulations by the Medical Dictionary for Regulatory Activities (MedDRA) system organ class and preferred term. Frequency tables of MDS classification according to WHO will be shown.

Previous and concomitant medications will be coded according to the WHO drug code and the Anatomical Therapeutic Chemical (ATC) Classification System. They will be summarized by type (e.g., previous, concomitant) by tabulating the number and percentages of patients.

Patient characteristics will be displayed by treatment regimen and overall.

10.7 Treatment compliance

The dose administered at each cycle for the treatment agent will be assessed and dose intensity will be summarized by treatment regimen. Details will be provided in the SAP.

10.8 Efficacy analysis

Definitions of primary and secondary endpoints are specified in section 2.3. Due to the change in treatment regimen, efficacy analysis will be done separated by treatment regimen.

10.8.1 Analysis of primary endpoint

The absolute and relative frequencies of overall hematological response as assessed in [REDACTED] of treatment with imetelstat will be evaluated using the FAS and repeated for the PPS. Treatment success will be determined by patients showing at least PR (CR, CRi or PR) and/or showing a hematologic improvement for one or several lines.

According to the previous design (see section 10.3), an absolute cut-off value was used to determine the study outcome at the interim and final analysis. Due to the changes described in section 5 and 7.1, the primary endpoint will only be analyzed in an exploratory way.

Summary statistics and an exact two-sided 90% confidence interval for overall hematological response rate using the Clopper-Pearson method will be presented.

10.8.2 Analysis of secondary endpoints

Secondary efficacy measurements include overall survival (OS), progression-free survival (PFS), time to treatment failure, duration of response, best overall response and response analysis based on the IWG 2023 criteria (for MDS population only). Moreover, Health-Related Quality of life will be evaluated using EORTC QLQ-C30 (version 3). Analyses of secondary endpoints will be performed in exploratory manners based on the FAS and separated by treatment regimen.

10.8.2.1 Overall survival

Overall Survival (OS) will be assessed using Kaplan-Meier method. The death of patient is regarded as the event of interest. The estimates obtained are invariably expressed in graphical form. Median survival time, the survival rate at week [REDACTED] and more additional timepoints (defined in SAP) with two-sided 95% confidence intervals (CI) using the complementary log-log transformation method will be tabulated.

10.8.2.2 Progression-free-survival

Kaplan-Meier method will be used to assess progression-free survival (PFS). Kaplan-Meier Curves depicting PFS will be generated. Additionally, median PFS, PFS rate at week [REDACTED] and more additional timepoints (defined in SAP) of treatment with imetelstat will be reported. The two-sided 95% confidence intervals (CI) for the median, week [REDACTED], and week [REDACTED] will be calculated using the complementary log-log transformation method. Detailed methodology is provided in the SAP.

10.8.2.3 Duration of response

Median time and 95% confidence interval for duration of response will be summarized using descriptive methods.

10.8.2.4 Best overall response

Best overall response at the end of treatment will be summarized. The summary table will include counts and percentages for each response category (CR, PR, SD etc. described in Appendix III, section 16.3).

10.8.2.5 Response based on IWG 2023

Response based on the updated IWG 2023 criteria at visit 9 will be analyzed only for MDS population. Absolute and relative frequencies will be provided for each category.

10.8.2.6 HRQoL

Health-Related Quality of Life (HRQoL) will be accessed using EORTC QLQ-C30, version 3. The raw score for global health status / QoL, functional scales and symptom scales / items will be summarized with descriptive statistics by visit. Moreover, the convert score will also be provided, more details will be described in the SAP.

10.8.3 Analysis of other efficacy variables

Transfusion data collected in eCRF will be analyzed using descriptive statistics by visits. More details will be provided in SAP.

10.9 Safety analysis

All safety analyses will be performed on the SES. At least summary statistics and, where meaningful, change from baseline will be reported. Full details will be included in the SAP. Safety analysis will be performed by treatment regimen and overall.

10.9.1 Toxicity analysis

Toxicity will be summarized during the study. Details will be provided in the SAP.

10.9.2 Extent of Exposure

Duration of treatment, total dose and dose intensity will be summarized. Dose modifications will also be summarized if applicable. Details will be provided in the SAP.

10.9.3 Adverse Events

Adverse events will be defined as treatment-emergent if they are newly occurring or worsen following treatment with imetelstat. For this trial, the only adverse events that will be counted will be TEAEs (see section 9.1.2). TEAEs will be classified by system organ class and preferred term using the Medical Dictionary for Regulatory Activities (MedDRA).

Tables for TEAEs will show the number and frequencies of incidences by severity and relation to IMP. Individual listings of AEs, SAEs and deaths within 30 days from last exposure to IMP will be generated.

TEAEs leading to premature discontinuation of study drug or withdrawal from the study will be summarized and listed in the same manner.

The percentage of patients with unacceptable toxicity acc. to CTCAE v5.0 criteria will be provided for week 4 (C4) and week 17 (beginning of C5, V9), and accompanying exact two-sided 95% confidence interval using the Clopper-Pearson method will be provided.

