Due to the transient improvement seen in WBC and peripheral blasts in patients early in treatment, it was accorded to continue the study in an exploratory approach with a change in dose frequency. Therefore, binomial test will be performed with a two-sided 90% confidence interval for overall haematological response rate using the Clopper-Pearson method for both treatment cohorts (see 2.7) independently. Analysis will be repeated by subgroups (see 4.2). A SAS pseudo code can be:

```
proc freq data=Data;
  by Treatment_cohort;
  tables Hematological_response / binomial(all level="0") alpha=0.1 cl ;
  exact binomial /point;
run;
```

Response assessments of visit 5(W9 C3) and visit 9(W17 C5) will be listed.

Table	
14.5.1	Overall hematological response rate
Figures	
14.5.1	Overall hematological response rate at beginning of cycle 5
Listing	
16.5.1	Response assessment

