### 8.5.2 Time and rate to first related TEAE with toxicity of grade 3 or higher

Time to first related TEAE with toxicity of grade 3 or higher acc. CTCAE v5.0 criteria as defined in section 7.7.13 will be evaluated using Kaplan-Meier method based on the SES. The estimates

obtained are invariably expressed graphically. Median survival time with two-sided 95% confidence intervals (CI) using the complementary log-log transformation method will be tabulated. Survival rate before week ■ (in ■■■■■) and week ■ (in ■■■■■) with exact two-sided 95% confidence interval using the Clopper-Pearson method will be provided.

Table	
14.7.6	Time and rate to first related TEAE with toxicity of grade 3 or higher
Figures	
14.7.6	Time to first related TEAE with toxicity of grade 3 or higher

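### The protocol's toxicity rate uses an event with no readable definition and an early time point that contradicts itself, and the SAP's matching rate counts related grade 3 or higher TEAEs without recording that choice

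*Protocol*

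**What the plan says.** Protocol section 10.9.3 closes its adverse event plan with a rate: "The percentage of patients with unacceptable toxicity acc. to CTCAE v5.0 criteria will be provided for week 4 (C4) and week 17", the latter labelled "beginning of C5, V9", and "accompanying exact two-sided 95% confidence interval using the Clopper-Pearson method will be provided". The paragraph just before it separately plans to summarise and list TEAEs that lead to stopping study drug or leaving the study.

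The SAP contains no rate of unacceptable toxicity. Its nearest counterpart is section 8.5.2: "Time to first related TEAE with toxicity of grade 3 or higher acc. CTCAE v5.0 criteria as defined in section 7.7.13 will be evaluated" by Kaplan-Meier in the Safety Evaluation Set (SES). That section adds a "Survival rate before week" (number blacked out) and at a second blacked-out week, "with exact two-sided 95% confidence interval using the Clopper-Pearson method will be provided". Section 7.7.13 defines the event as the first TEAE of grade 3 or higher judged possibly related, probably related or related.

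SAP section 6.2.2 also sets an early-toxicity cut at visit 3, labelled week 5, cycle 2. SAP section 9, on changes to the planned analysis, mentions only overrunning of the study population.

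**The concern.** The event has no fixed meaning. CTCAE assigns grades; it does not call any grade unacceptable. The readable protocol uses the phrase otherwise only as a ground for ending treatment (for example sections 5.1, 5.1.2, 5.1.4 and 8.1.6). A reader cannot tell whether the SAP defined the protocol's rate, replaced it or dropped it.

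The choice of event matters in this population. Inclusion criterion 5 requires at least one cytopenia, and protocol section 7.2.2.1 names cytopenias as the primary dose-limiting toxicities of the drug. Disease and drug effects are therefore hard to separate. A related-only count rests on the investigator's attribution, with no control arm to check it. Safety is tabulated by regimen, and the second regimen doses more often, so this rate will be read across the two cohorts.

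The early time point is also unclear, because week 4 and cycle 4 cannot be the same time.

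**Working it through.** **Event, side by side**

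| | Protocol 10.9.3 | SAP 8.5.2 and 7.7.13 |
|---|---|---|
| Event | unacceptable toxicity by CTCAE v5.0 | TEAE of grade 3 or higher |
| Attribution | none stated | judged related |
| Quantity | percentage affected | event-free rate |
| Interval | exact 95% Clopper-Pearson | the same |
| Times | week 4 (C4) and week 17 (C5) | two weeks, both blacked out |

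Related grade 3 or higher events are a subset of all grade 3 or higher events, so the related-only percentage cannot be the larger. How far apart they are cannot be derived from the documents. With an assumed 20 patients in a cohort, each patient whose classification changes moves the rate by 1/20 = 5 percentage points.

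**Calendar**

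Inputs: week 5 = C2 (SAP 6.2.2); week 9 = C3 and week 17 = C5 (SAP 8.3: "Response assessments of visit 5(W9 C3) and visit 9(W17 C5) will be listed"); week 17 = "beginning of C5, V9" (protocol 10.9.3).

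Week w starts on day 7(w − 1) + 1, and cycle c of length L days starts on day L(c − 1) + 1. Taking each labelled visit as day 1 of its cycle:

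- week 5 = C2: 28 = L
- week 9 = C3: 56 = 2L
- week 17 = C5: 112 = 4L

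All three give L = 28. A search over every length from 7 to 42 days found no other that fits.

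With 28-day cycles, week w lies in cycle floor((w − 1)/4) + 1.

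- Week 17: floor(16/4) + 1 = 5. The protocol's second label is reproduced.
- Week 4: floor(3/4) + 1 = 1, not 4.
- Cycle 4 starts on day 3 × 28 + 1 = 85 (week 13) and ends on day 112 (week 16).

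Other lengths do not rescue the label. One-week cycles put week 4 in C4 but week 17 in C17. Two-week cycles give C2 and C9; three-week cycles give C2 and C6. The cycle row of the protocol's Part 1 schedule looks damaged in the public copy and was not used. Read literally it would put cycle 4 at week 7, so week 4 would still not be C4.

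The SAP's early cut, visit 3 in week 5, is day 29. Events before it fall on days 1 to 28, that is, through the end of week 4.

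**Size of the label ambiguity**

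Assume a constant hazard and a proportion p affected by the start of week 17 (16 weeks elapsed). Then h = −ln(1 − p)/16, and the proportion affected by t weeks is 1 − exp(−ht). Compare t = 4 (end of week 4) with t = 12 (start of cycle 4).

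| Assumed p | 4 weeks | 12 weeks | Difference (points) |
|---|---|---|---|
| 40% | 12.0% | 31.8% | 19.8 |
| 60% | 20.5% | 49.7% | 29.2 |
| 80% | 33.1% | 70.1% | 37.0 |

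For these rates the standard error √(r(1 − r)/20), with r the rate and an assumed 20 patients, is 7 to 11 points. If C4 meant the end of cycle 4, day 112, the early time point would fall together with the week 17 one.

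**The case against.** The strongest reply is that the SAP did what it was asked to do. Protocol sections 10.9 and 10.9.1 leave toxicity details to the SAP, and a working definition for a loose term is such a detail. Grade 3 is a sensible cut, since protocol section 7.1 ties dose delay or reduction to grade 3 or 4 toxicity. A threshold for unacceptable toxicity may stand in the blacked-out dose-modification tables. The related category is broad: it includes possible, and SAP 7.7.12 also counts a missing assessment. SAP 8.5.1 already tabulates TEAEs by grade, by relationship and by early toxicity. The whole analysis is exploratory, and no decision rule uses this rate.

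Much of this stands, and it keeps the point modest. It does not settle it. The SAP never says that its event is meant to define the protocol's, and section 9 is silent. The grade table is broken down by SOC and PT. No planned output gives a patient-level, any-relationship grade 3 or higher percentage at a fixed time with an interval.

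A reader might infer three stronger things that the documents do not support.

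- That the two documents use different time points. The weeks in SAP 8.5.2 are blacked out and cannot be compared. The one readable SAP cut, before visit 3, fits a plain reading of week 4, so C4 may be only a wrong label.
- That unacceptable toxicity simply means toxicity leading to discontinuation. The phrase is used that way elsewhere, but section 10.9.3 plans a discontinuation summary separately and then adds this rate as something else.
- That the related-only event was chosen to give a better-looking figure. Nothing in the documents shows this.

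**Conclusion.** Two things hold. The protocol's event is undefined in the readable text and does not match the event of the only comparable SAP rate, and the SAP does not record the choice. The protocol's early time point is self-contradictory under its own week 17 label and under every readable SAP anchor.

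The 20 to 37 point range rests on a constant hazard and assumed week 17 proportions of 40% to 80%. It measures how much the protocol sentence leaves open, not a discrepancy between protocol and SAP. The effect of the change of event cannot be sized from the documents; only its direction between related and any-relationship counts is certain.

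This concerns a secondary safety measure in an exploratory trial, so it does not threaten the main result. It should still be corrected before database lock, because as written the same data could be reported as several different rates.

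**What to change.** 1. Use one event definition in protocol 10.9.3 and SAP 8.5.2. It should also settle missing relationship, which SAP 7.7.12 counts as related but the formula in 7.7.13 leaves out.
2. Correct the week and cycle label, and state the same fixed study days in both documents. If plain week 4 was meant, days 1 to 28 match the SAP's early cut before visit 3; week 17 then means through day 112, before visit 9.
3. By cohort in the SES, report the percentage of patients with at least one grade 3 or higher TEAE of any relationship by each day, beside the related-only percentage, both with exact 95% intervals. Use crude percentages, since the Clopper-Pearson interval needs a count and a denominator.
4. Tabulate TEAEs leading to discontinuation as well as listing them. Protocol 10.9.3 already promises a summary, while SAP 8.5.1 plans only Listing 16.7.3. Do not label this table as unacceptable toxicity.
5. Record the definition in SAP section 9.

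The cost is wording in both documents and a few table rows, from data already collected and with no change to patient management. The any-relationship figure cannot be lower than the related-only one and will probably look less favourable.
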